4.3.1.1.2 Maximum Intensity

Maximum overall intensity is derived from the daily intensities computed as described in [Section 4.3.1.1.1](#) and is calculated as the maximum of the daily intensities over the period considered.

4.3.1.1.3 Presence

Presence is derived from the maximum overall intensity over the time period considered:

- None: No presence
- Grade 1, Grade 2, or Grade 3: Presence
- Missing or Unknown: Missing presence

Subjects with at least one non-missing presence for a specific endpoint will be included in the analysis. Conversely, those without a non-missing presence will not be included in the analysis of the endpoint.

The time period is displayed as D0-D3, D4-D7, D8 and later.

4.3.1.1.4 Time of Onset

Time of onset is derived from the daily intensities computed as described in [Section 4.3.1.1.1](#). It corresponds to the first day with intensity of Grade 1, Grade 2, or Grade 3.

Note: If a reaction is not continuous (i.e., reaction occurs over two separate periods of time intervened by at least one daily intensity Missing or None) then the time of onset is the first day of the first occurrence.

4.3.1.1.5 Number of Days of Occurrence During the Solicited Period

Number of days of occurrence over the period considered is derived from the daily intensities computed as described in [Section 4.3.1.1.1](#). It corresponds to the number of days with daily intensities of Grade 1, Grade 2, or Grade 3. Number of days of occurrence on the solicited period with a specified intensity may also be derived.

4.3.1.1.6 Overall Number of Days of Occurrence

If a reaction is ongoing at the end of the solicited period, then the overall number of days of occurrence is derived from the daily intensities and the end date of the reaction after the end of the solicited period.

The overall number of days of presence is:

$$\begin{aligned} & (\text{End date} - \text{last vaccination date}) + (\text{number of days of occurrence within the solicited period}) \\ & - \text{length of the solicited period} + 1 \end{aligned}$$

If the end date is missing or incomplete (contains missing data), the overall number of days of occurrence will be considered as Missing.

4.3.1.1.7 Ongoing

Ongoing is derived from the last daily intensity of the solicited period computed as described in [Section 4.3.1.1.1](#) and the maximum intensity on the ongoing period. The investigator's ongoing flag is not used because the measurement would determine the ongoing status of the reaction.

- Ongoing: if the last daily intensity of the solicited period is at least Grade 1 and the maximum intensity on the ongoing period is at least Grade 1
- Not ongoing: if the last daily intensity of the solicited period is None or the maximum intensity on the ongoing period is None.
- Missing: all other conditions (in this case, it is not included in the denominator of the ongoing analysis in the safety tables).

4.3.1.2 Unsolicited AEs

Unsolicited AEs includes both serious (SAEs) and non-serious unsolicited AEs.

4.3.1.2.1 Presence

An observation will be considered an event if it has at least a verbatim term and is not a Grade 0 intensity event.

Grade 0 events are not included in safety analysis but are included in separate listings.

4.3.1.2.2 Intensity

Intensity will be defined according to the following classification: None, Grade 1, Grade 2, Grade 3, or Missing.

If the unsolicited AE is measurable and its preferred term is part of the list of solicited reactions, then the measurement is derived based upon and following the same rule of the intensity scales defined in the [Table 4.1](#) and [Table 4.2](#) for that measurable injection site or systemic reaction. Note the intensity could be considered as “None” (not a reaction) in the analysis despite being considered a reaction by the investigator (e.g., swelling measurement >0 mm but <25 mm in adults).

Intensity for the other unsolicited AEs will correspond to the value reported in the CRF.

The maximum intensity corresponds to the highest intensity for a unique term.

4.3.1.2.3 Last Vaccination

Since there is only one vaccination in this study, last vaccination before an unsolicited AE is the study vaccination at V01.

4.3.1.2.4 Time of Onset

Time of onset is derived from the start date of the unsolicited AE and the date of last vaccination as described in [Section 4.3.1.2.3](#):

Time of Onset = start date of the unsolicited AE – date of last vaccination before the unsolicited AE

The time of onset is considered as missing only if one or both of the dates are missing or partially missing.

The unsolicited AEs will be analyzed “Within 30 days” after each vaccination, which corresponds to AEs with a time of onset between 0 and 30 days after vaccination or missing. An AE with missing time of onset will be considered to have occurred just after the last vaccination (computed according to the [Section 4.3.1.2.3](#)), so will be included in these tables.

Time of onset period is displayed as D0-D3, D4-D7, D8-D14, D15 or later, and Missing.

Note: Unsolicited AE that occurred before vaccination (negative time of onset) or with a time of onset higher than defined above will not be included in analysis but will be listed separately.

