4.3.1.3 Serious Adverse Events

An event will be considered as a serious event if “Yes” is checked for “Serious” in the CRF. SAEs will be analyzed throughout the study using the following periods:

- Within 7 days after vaccination
- Within 30 days after vaccination
- During the study (i.e., all SAEs occurred during the study)

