5.3.1.4 Start Date and End Date

Missing or partially missing start dates or end dates for unsolicited AEs (including SAEs) will remain missing and not be imputed. If the start date is missing or partially missing, the time of onset will be considered to be missing. Nevertheless unsolicited AEs with missing time of onset will be included in analyses according to the last vaccination (computed according to the [Section 4.3.1.2.3](#)). If either the start date or end date is missing or partially missing, the duration will be considered missing.

Missing or partially missing end dates for ongoing solicited AEs will remain missing and not be imputed.

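### A partly recorded AE start date is treated as wholly unknown, so events whose recorded month rules out D0–D30 are still counted within 30 days of vaccination

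*SAP*

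**What the plan says.** SAP 4.3.1.2.4 computes time of onset as AE start date minus vaccination date. On incomplete dates it says: "The time of onset is considered as missing only if one or both of the dates are missing or partially missing". SAP 5.3.1.4 agrees: "If the start date is missing or partially missing, the time of onset will be considered to be missing". It also rules out completing the date: "Missing or partially missing start dates or end dates for unsolicited AEs (including SAEs) will remain missing and not be imputed".

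These events are then kept in the analysis. The 30-day window is defined as one "which corresponds to AEs with a time of onset between 0 and 30 days after vaccination or missing", and the reason given is: "An AE with missing time of onset will be considered to have occurred just after the last vaccination". SAP 5.3.1.4 confirms it: "Nevertheless unsolicited AEs with missing time of onset will be included in analyses according to the last vaccination".

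A note at the end of 4.3.1.2.4 points the other way for events known to lie outside the window: "Unsolicited AE that occurred before vaccination (negative time of onset) or with a time of onset higher than defined above will not be included" in the analysis; they go to a separate listing.

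The same section gives the onset breakdown its own 'Missing' band. SAP 4.3.1.3 and 4.3.1.4 report SAEs and AESIs in three periods ("Within 7 days after vaccination", the same for 30 days, and the whole study), with no rule of their own for incomplete dates.

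**The concern.** Placing an event of unknown date just after vaccination is a sensible, cautious choice. A partial date is not always unknown in the sense that matters, however. When only the day is missing, the month and year may show that the event started before vaccination or after D30. The SAP discards that information and counts the event inside the window. The note that should send it to a listing relies on a negative or too-large onset, and no onset is computed for a partial date.

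At stake are the windowed safety percentages, above all rows with few or no events, where one misplaced subject is visible. Two programmers could also handle the same record differently, because the order of the two rules is not stated.

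**Working it through.** The documents give no figure on this point, so there is none to reproduce. The check applies the rule to calendar dates and then sizes the effect.

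**Inputs**
- 30-day window: D0 to D30, or onset missing (SAP 4.3.1.2.4).
- Visit 2 falls 30 to 44 days after vaccination (SAP 3.2), so onsets on D31 to D44 can be collected.
- Planned inclusion period: April 2019 to June 2021 (Protocol 5.1.5).
- Enrolled: 290 (SAP 5.7.2). The size of the safety analysis set is not stated; 290 is used as an assumption.
- Number of AEs with a partial start date: not stated; 1 to 5 subjects assumed for illustration.

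**Step 1: dates that the recorded month settles.** Earliest onset = first day of the recorded month − vaccination date. Latest onset = last day of that month − vaccination date.
- Vaccination 15 May 2019, start 'April 2019': day −44 to day −15. Certainly before vaccination; counted within 30 days.
- Vaccination 1 May 2019, start 'June 2019': D30 is 31 May and 1 June is D31. Certainly after the window; counted within 30 days.
- Vaccination 20 May 2019, start 'July 2019': D30 is 19 June and 1 July is D42. Certainly after the window; counted within 30 days.

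**Step 2: dates that it leaves open.** For vaccination on 15 May 2019, 'May 2019' spans day −14 to D16 and 'June 2019' spans D17 to D46. Both are compatible with the window, so counting them is the cautious choice and should stay.

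**Step 3: how often the late case can arise.** Take every vaccination day from 1 April 2019 to 30 June 2021 and ask whether some date on D31 to D44 falls in a calendar month that begins after D30. The answer is yes for 377 of 822 days: 377/822 = 46%. If onsets were spread evenly over D31 to D44 and over vaccination days, about 25% of these late onsets would be recognisable from the month alone.

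**Step 4: size.** Percentages are of subjects, so a subject adds 1/290 = 0.34 percentage points to a row only if no other event already places that subject in it. Exact (Clopper-Pearson) 95% intervals, n = 290:

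| Subjects in row | % | 95% CI |
|---|---|---|
| 0 | 0 | 0 to 1.26 |
| 1 | 0.34 | 0.01 to 1.91 |
| 3 | 1.03 | 0.21 to 2.99 |
| 5 | 1.72 | 0.56 to 3.98 |

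For the zero row the upper limit is 1 − 0.025^(1/290) = 1.26%.

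**The case against.** The strongest reply is that this is a deliberate cautious convention with little practical reach. Much of that stands.

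- **Few such records are likely.** AEs are collected from Visit 1, where consent and vaccination both take place, and pre-existing conditions are not reported as AEs unless they worsen (Protocol 5.1.4, 9.2.1). Start dates are required (9.2.3.3), diary gaps are clarified with the subject (13.2), and data are checked and queried (11.2). SAEs are reported within 24 hours (10.1) and reconciled before database release (11.2). A month-only SAE date surviving all this would be unusual.
- **The direction is cautious.** The rule over-counts AEs in a single-arm descriptive study without hypotheses. No test or power is affected.
- **The onset breakdown has a 'Missing' band.** A reader might infer that these events would appear as D0–D3. The SAP does not support that; the effect is on the windowed counts.
- **The two rules need not collide.** A reader might infer that the SAP flatly contradicts itself. The note ties its pre-vaccination exclusion to a negative onset, which a partial date never yields, while the missing-onset rule covers such dates explicitly. This is an unstated order of precedence rather than a contradiction.

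What does not stand is the use of caution to defend the settled cases. Where the recorded month rules out D0–D30, nothing is uncertain about the window, and counting the event there is simply wrong.

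**Conclusion.** The point holds as a minor one. Read literally, SAP 4.3.1.2.4 and 5.3.1.4 count within 30 days some events whose recorded month and year place them before vaccination or after D30, although the note in 4.3.1.2.4 intends such events to be listed.

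The size is 0.34 percentage points per affected subject, assuming that the safety set is about 290 and that the subject has no other event in the row. The number of affected subjects is unknown and probably very low.

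A reader might also infer that a late SAE or AESI with a partial date would definitely fall in the 7-day row. That goes further than the text. SAP 4.3.1.3 and 4.3.1.4 have no missing-onset rule, and the 'just after' sentence is written for the 30-day tables. SAP 5.3.1.4 does extend the handling of partial dates to SAEs, so placement in the 7-day and 30-day SAE and AESI rows is a possible inference, and the SAP should settle it.

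**What to change.** Amend SAP 4.3.1.2.4 and 5.3.1.4 so that the earliest and latest possible start dates are derived from the recorded part of the date before onset is declared missing. Then:

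1. If the latest possible date is before vaccination, list the event as pre-vaccination and leave it out of the analysis.
2. If the earliest possible date is after the end of a window (7 or 30 days), do not count the event in that window. SAEs and AESIs stay in the 'During the study' row.
3. Otherwise, keep the present convention.

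State that these steps take precedence over the missing-onset rule and that they also govern SAP 4.3.1.3 and 4.3.1.4.

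The cost is one SAP paragraph and a few lines of programming, with no new data. The change should be in place before the first of the two analysis steps in SAP 5.7.1, because that step covers safety and its data are then final.

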	
Safety
 
 Occurrence, nature (Medical Dictionary for Regulatory Activities [MedDRA] preferred term), duration, intensity, relationship to vaccination, and whether the event led to early termination for the study of any unsolicited systemic AEs reported in the 30 minutes after vaccination. Occurrence, time of onset, number of days of occurrence, intensity, action taken, and whether the reaction led to early termination from the study, of solicited (prelisted in the subject's diary card and electronic case report book [CRB]) injection site reactions occurring up to 7 days after vaccination. Occurrence, time of onset, number of days of occurrence, intensity, action taken, and whether the reaction led to early termination from the study, of solicited (prelisted in the subject's diary card and CRB) systemic reactions occurring up to 7 days after vaccination. Occurrence, nature (MedDRA preferred term), time of onset, duration, intensity, action taken, relationship to vaccination (for systemic AEs only), and whether the event led to early termination from the study, of unsolicited non-serious AEs occurring up to Visit 2. Occurrence, nature (MedDRA preferred term), time of onset, duration, seriousness criteria, relationship to vaccination, outcome, and whether the SAE led to early termination from the study, of SAEs (including AESIs) throughout the trial.
Planned Sample Size:	
A total of 330 subjects are planned to be enrolled with an expected dropout rate of 15% (280 evaluable subjects planned).
 
In order to balance the age of subjects at enrollment, between 50 and 130 enrolled subjects should be ≥ 75 years of age.

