5.1.3 Study Plan

Vaccination

All subjects will receive a single dose of MenACYW conjugate vaccine at Visit 1 (D0).

Blood sampling

All subjects will provide a pre-vaccination blood sample at Visit 1 and a post-vaccination sample at Visit 2 (30 to 44 days after the vaccination at Visit 1).

Collection of safety data

- All subjects will be followed for safety from Visit 1 (D0) to Visit 2.
- All subjects will be observed for 30 minutes after vaccination, and any unsolicited systemic AEs occurring during that time will be recorded as immediate unsolicited systemic AEs in the case report book (CRB).
- The subject will record information in a diary card about solicited reactions from D0 to D07 after vaccination and unsolicited AEs from D0 to Visit 2.

- SAEs (including AESIs) will be recorded throughout the duration of the trial. The subject will record information in a diary card about SAEs from D0 to Visit 2.
- The subject will be asked to notify the site immediately about any potential SAEs at any time during the trial.
- Staff will contact the subjects by telephone on D08 (+2 days) to identify the occurrence of any SAE not yet reported and to remind them to complete the diary card up to Visit 2 and to bring it back to Visit 2.
- The completed diary card will be reviewed with the subject at Visit 2.

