9.2.2 Safety Endpoints

The endpoints for the evaluation of safety are:

- Occurrence, nature (Medical Dictionary for Regulatory Activities [MedDRA] preferred term), duration, intensity, relationship to vaccination, and whether the event led to early termination from the study of any unsolicited systemic AEs reported in the 30 minutes after vaccination.
- Occurrence, time of onset, number of days of occurrence, intensity, action taken, and whether the reaction led to early termination from the study, of solicited (prelisted in the subject's diary card and electronic case report book [CRB]) injection site reactions occurring up to 7 days after vaccination.
- Occurrence, time of onset, number of days of occurrence, intensity, action taken, and whether the reaction led to early termination from the study, of solicited (prelisted in the subject's diary card and CRB) systemic reactions occurring up to 7 days after vaccination.
- Occurrence, nature (MedDRA preferred term), time of onset, duration, intensity, action taken, relationship to vaccination (for systemic AEs only), and whether the event led to early termination from the study, of unsolicited AEs occurring up to Visit 2.

- Occurrence, nature (MedDRA preferred term), time of onset, duration, seriousness criteria, relationship to vaccination, outcome, and whether the SAE led to early termination from the study, of SAEs (including AESIs) throughout the trial.

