9.2.3 Safety Assessment Methods

At Visit 2, the Investigator or a delegate will ask the subject about any solicited reactions and unsolicited AEs recorded in the diary card, as well as about any other AEs that may have occurred since the previous visit. All relevant data will be transcribed into the CRB according to the instructions provided by the Sponsor.

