9.2.3.3 Unsolicited Adverse Events

In addition to recording solicited reactions, subjects will be instructed to record any other medical events that may occur during the 30-day period after vaccination. Space will be provided in the diary card for this purpose.

Information on SAEs will be collected and assessed throughout the study, from the time of vaccination until 30 days (+14 days) after vaccination. Any SAE occurring at any time during the study will be reported by the Investigator in the CRB according to the completion instructions provided by the Sponsor; this includes checking the “Serious” box on the AE CRF and completing the appropriate Safety Complementary Information CRFs. All information concerning the SAE is to be reported either as part of the initial reporting or during follow-up reporting if relevant information became available later (eg, outcome, medical history, results of investigations, copy of hospitalization reports).

For each unsolicited AE (whether serious or non-serious), the following information is to be recorded:

- Start and stop dates^a
- Intensity of the event:

For measurable unsolicited AEs that are part of the list of solicited reactions, the size of the AE as well as the temperature for fever will be collected and analyzed based on the corresponding scale used for solicited reactions (see [Table 9.1](#) and [Table 9.2](#)).

All other unsolicited AEs will be classified according to the following intensity scale:

- Grade 1: A type of adverse event that is usually transient and may require only minimal treatment or therapeutic intervention. The event does not generally interfere with usual activities of daily living.
- Grade 2: A type of adverse event that is usually alleviated with additional therapeutic intervention. The event interferes with usual activities of daily living, causing discomfort but poses no significant or permanent risk of harm to the research participant.

^a The stop date of all related AEs will be actively solicited. For other events, the investigator will provide the stop date when it becomes available. AEs for which no stop date was obtained during the course of the study will be considered as ongoing at the end of the study.

- Grade 3: A type of adverse event that interrupts usual activities of daily living, or significantly affects clinical status, or may require intensive therapeutic intervention.
- Whether the AE was related to the investigational product (for unsolicited systemic AEs)

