4.2 Safety

The following endpoints will be used for all subjects for the evaluation of safety:

- Unsolicited systemic AEs reported in the 30 minutes after the vaccination, including occurrence, nature (Medical Dictionary for Regulatory Activities [MedDRA] preferred term), duration, intensity, relationship to the product administered, and whether the event caused termination from the study.
- Solicited (prelisted in the subject's diary card and CRB) injection site and systemic reactions starting any time from Day 0 (day of vaccination) through Day 7 after the vaccination, including occurrence, time of onset, number of days of occurrence, intensity, action taken, and whether the reaction caused termination from the study.
- Unsolicited AEs occurring up to Visit 2, including occurrence, nature (MedDRA preferred term), time of onset, duration, intensity, action taken, relationship to the product administered (for systemic AEs only), and whether the event caused termination from the study.

- SAEs (including AESIs) reported throughout the trial, including occurrence, nature (MedDRA preferred term), time of onset, duration, seriousness criteria, relationship to the product administered, whether the event caused termination from the study, outcome.

See Section 9.2 of the protocol for more details.

[Table 4.1](#) and [Table 4.2](#) present, respectively, the injection site reactions and systemic reactions that are prelisted in the diary cards and CRB, together with the intensity scales.

Table 4.1: Solicited injection site reactions: terminology, definitions, and intensity scales

CRB term (MedDRA lowest level term [LLT])	Injection site pain	Injection site erythema	Injection site swelling
MedDRA preferred term (PT)	Injection site pain	Injection site erythema	Injection site swelling
Diary card term	Pain	Erythema	Swelling
Definition	Pain either present spontaneously or when the injection site is touched or injected limb is mobilized	Presence of a redness including the approximate point of needle entry	Swelling at or near the injection site. Swelling or edema is caused by a fluid infiltration in tissue or cavity and, depending on the space available for the fluid to disperse, swelling may be either soft (typically) or firm (less typical) to touch and thus can be best described by looking at the size of the swelling.

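### Non-serious unsolicited AEs starting between Day 31 and Visit 2 are listed but left out of the AE rates, so the endpoint defined up to Visit 2 is not estimated as stated

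*SAP*

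**What the plan says.** **Endpoint.** SAP 4.2 lists "Unsolicited AEs occurring up to Visit 2, including occurrence, nature" and further attributes. Protocol 9.2.2 gives the same window, "of unsolicited AEs occurring up to Visit 2", and the endpoints in the Protocol synopsis name the non-serious events: "of unsolicited non-serious AEs occurring up to Visit 2". Visit 2 is 30 to 44 days after vaccination (Protocol 5.1.3, SAP 3.2).

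**Collection.** Under Protocol 5.1.3 the diary covers "solicited reactions from D0 to D07 after vaccination and unsolicited AEs from D0 to Visit 2". At Visit 2 the site asks about diary entries, "as well as about any other AEs that may have occurred since the previous visit" (Protocol 9.2.3). One sentence differs: Protocol 9.2.3.3 tells subjects to record "any other medical events that may occur during the 30-day period after vaccination".

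**Analysis.** SAP 4.3.1.2.4 defines a single period for unsolicited AEs, within 30 days, "which corresponds to AEs with a time of onset between 0 and 30 days after vaccination or missing". Its closing note says that an AE before vaccination "or with a time of onset higher than defined above will not be included in analysis but will be listed separately". SAP 4.3.1.3 and 4.3.1.4 give SAEs and AESIs three periods: 7 days, 30 days and the whole study.

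**The concern.** The SAP sets an endpoint in one section and tabulates a shorter one in another. A non-serious, non-AESI event that starts on Day 31 or later falls inside the endpoint and inside planned data collection, yet it enters no percentage and no confidence interval. This applies equally to related and Grade 3 events. SAP Table 5.1 promises the number, percentage and 95% CI of subjects, and the number of events, for unsolicited AEs. A reader of the report would take the 30-day figure to be the endpoint. The omission works in one direction only: it can lower the rate relative to the stated endpoint but cannot raise it. The treatment of dates is also uneven, because an AE with a missing onset date is counted while one with a known onset on Day 31 to 44 is not.

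**Working it through.** **Does another part of the plan close the gap?**

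| Event with onset after Day 30 | Planned treatment | Source |
|---|---|---|
| SAE | Analysed over the whole study | SAP 4.3.1.3 |
| AESI | Analysed over the whole study | SAP 4.3.1.4 |
| AE leading to discontinuation | Counted through the end-of-study form in the disposition and overview tables; the SOC/PT table depends on the time window | SAP 4.3.1.5.6 |
| Any other unsolicited AE | Listing only | SAP 4.3.1.2.4 |

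The onset display category that begins at Day 15 has no upper day. It belongs to the 30-day analysis, however, and the note that follows it excludes later onset, so it does not bring these events back. SAP 5.7 records changes to analysis timing, sample size and reportable medications, but not this restriction.

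**Size of the uncounted window.** Let *v* be the day of Visit 2, from 30 to 44. Followed days are *v* + 1, counting Day 0, and uncounted days are *v* − 30.

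- *v* = 30: 0/31 = 0%
- *v* = 37: 7/38 = 18.4%
- *v* = 44: 14/45 = 31.1%
- *v* uniform over the 15 days (assumption): 105/570 = 18.4%

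**Possible effect on the reported scale (percentage of subjects).** The plan states no AE rate, so the 30-day rates below are assumptions. With a constant rate of first AE (also an assumption) and a 30-day rate *p*₃₀ over 31 days:

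*p*(*v*) = 1 − (1 − *p*₃₀)^((*v* + 1)/31)

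For example, with *p*₃₀ = 10% and *v* = 44: 1 − 0.9^(45/31) = 14.2%. The uniform column averages *p*(*v*) over Day 30 to 44. Extra subjects are 290 × (*p* − *p*₃₀), where 290 is the number enrolled (SAP 5.7.2).

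| Assumed 30-day rate | All visits Day 30 | Uniform | All visits Day 44 | Exact 95% CI for the 30-day rate |
|---|---|---|---|---|
| 10% (29/290) | 10.0% | 12.1% (6.1 more subjects) | 14.2% (12.1 more) | 6.8% to 14.0% |
| 30% (87/290) | 30.0% | 35.3% (15.5 more) | 40.4% (30.2 more) | 24.8% to 35.6% |

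In both rows the uniform figure lies inside the Clopper-Pearson interval and the Day 44 figure lies above its upper limit.

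**The case against.** The strongest defence is that 30 days is a legitimate window with a source in the Protocol. Protocol 9.2.3.3 gives subjects a 30-day instruction, Protocol 12.1 leaves analysis conventions to the SAP, and Protocol 12.1.1.2 sets no AE period. A fixed window also gives equal planned follow-up, whereas a rate to Visit 2 mixes 30 to 44 days and may rest on incomplete diaries after Day 30. Most of the weighty late events are covered, nothing is lost because late events are listed, and Day 0 to 30 is estimated with confidence intervals. The size depends wholly on assumptions: Visit 2 is targeted at Day 30, so clustering near that day would shrink the gap, and AEs concentrated soon after vaccination would shrink it further. Finally, 290 is the number enrolled, not the safety-set denominator.

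Much of this stands. The 30-day table is sound in itself, the two windows coincide for any subject seen on Day 30, and the figures above are illustrations. The defence still does not remove the mismatch. The 30-day sentence is a recording instruction, not an endpoint definition, and it conflicts with Protocol 5.1.3. If the SAP meant to adopt it, SAP 4.2 should not still run to Visit 2. A listing does not supply the rate and interval that SAP Table 5.1 promises.

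**Conclusion.** The concern holds. Followed as written, the SAP does not estimate its own unsolicited AE endpoint for non-serious, non-AESI events in subjects whose Visit 2 falls after Day 30. The missing part is the rate and interval for the full window to Visit 2.

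The share of follow-up left out is bounded by the visit window, between 0% and 31% per in-window subject. The effect on rates cannot be derived from the documents. Under the assumed constant rate and uniform visits it stays within sampling error, and it exceeds the upper confidence limits only in the extreme case of every visit on Day 44. The trial is single-arm and tests no hypothesis, so no conclusion or decision rule changes. It should be fixed because describing safety is a stated objective and the correction is cheap.

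**What to change.** 1. In SAP 4.3.1.2.4, add a whole-study period (Day 0 to Visit 2) for all unsolicited AEs, as already planned for SAEs and AESIs. Apply it to the overview, SOC/PT, related, Grade 3 and discontinuation tables.
2. Keep the 30-day period as the equal-exposure table.
3. Record the change in SAP 5.7.
4. Reconcile the recording period in Protocol 9.2.3.3 with Protocol 5.1.3. Enrolment is already reported in SAP 5.7.2, so this cannot alter what was recorded. The SAP should therefore state that diary entries after Day 30 may be less complete where subjects were given the 30-day instruction.

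If the 30-day rate is what the sponsor wants, the alternative is to restate the endpoint in SAP 4.2 as 30 days and record that in SAP 5.7 as a change from the Protocol.

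The main option costs SAP wording and one extra set of tables from data already collected. Its drawbacks are unequal follow-up in the added tables, which the retained 30-day table covers, and possible under-recording after Day 30, which the Visit 2 interview covers in part. The alternative costs wording only.
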